3.2. Endpoints

3.2.1. Primary endpoint

The primary endpoint is a composite endpoint defined as the percentage of patients:

- Losing at least 4 g/dl of Hb, within the 48 hours following IMP administration and/or
- Requiring the transfusion of at least 2 units of packed RBCs within the 48 hours following the administration of IMP.

The reference of Hb level is the most recent Hb value recorded within the third trimester of pregnancy.

The 4-g/l threshold has been used to define the severity of PPH in several studies (16,19). The determination of Hb level during the third trimester is mandatory in France and is independent of delivery, PPH and vascular loading. It is the reason why it was chosen preferably to Hb at the time of the inclusion.

The Hb might be modified by transfusion therefore transfusion is also included in the composite endpoint. The amount of transfusion is physician dependent and it is the reason why it has been decided not to use this sole criterion, and in addition, a minimum of 2 packs of RBCs has been defined. The 48-hour follow-up duration is chosen according to Ozier et al (36) because of the stabilisation of the hemoconcentration after PPH. In order to determine the time point evaluation at 48 hours after delivery (H48), a 20-hour time interval (from H32 to H52) will be allowed to show more flexibility towards the variability of the time of delivery and the hour of IMP administration (H0).

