8.2. Schedule of visits

The duration of patient participation is 6 ± 2 weeks starting from randomisation. After enrolment, all patients will be treated with IMP. The start of IMP administration corresponds to H0.

8.2.1. Visit 1: Inclusion / Blood sampling 1

Information on the study will be given at the moment of the diagnosis of haemorrhage (see Section 8.1.1).

- Informed consent must be obtained before any study procedure;
- Eligibility criteria check (inclusion and non-inclusion criteria);
- Date and start time of prostaglandin infusion;
- Demographics (height, weight prior to pregnancy and last known weight);
- Thromboembolic and obstetrical events and any clinically relevant medical conditions;
- Pregnancy parameters:
 - Hb level during the third trimester,
 - Hb level at the sixth month,
 - Ht and platelets will be collected if available
 - Date of last menstrual period, gestational age,
- Delivery parameters
 - Times of the start and the end of delivery;
 - Number of live births and/or stillbirths;
 - Procedures: artificial delivery, uterine or genital examination
- Prior and concomitant treatment (see Section 7) including intravenous fluids and blood products since the start of delivery;
- Haemorrhage parameters :
 - Haemorrhage start time;
 - Measured or estimated volume of blood loss at the start of prostaglandin infusion;
- Physical examination will include a comprehensive standard evaluation of all systems: cardiovascular system, respiratory system, skin and appendices, gastrointestinal system, ear-

nose-throat, lymphatic nodes, spleen, central nervous system, eyes, musculoskeletal system, endocrine system, argental system, psychiatric state. Signs for possible thrombosis will be checked.

- Vital signs:
 - Measurement of arterial blood pressure (systolic and diastolic),
 - Heart rate.
- Blood sampling for laboratory parameters at inclusion:
 - Complete blood count, Hb, Ht, platelets,
 - Haemostatic profile: fibrinogen, PT, QT, aPTT, D-dimers,
 - Blood urea and serum creatinine.

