- Single or multi-organ failure (SOFA score) in women transferred to resuscitation and/or intensive care and/or PICU and/or continuous care units.
- Death during the study.

1.10.2.5 *Biological effects of fibrinogen concentrate administration*

- Change in plasma fibrinogen level between H0 (start if IMP infusion) and D2;
- Evolution of hemoconcentration between H0 and D2
 - Change in Hb level between each determination and H0
 - Change in Ht level between each determination and H0
 - Change in RBCs count between each determination and H0

1.10.2.6 *Tolerance of fibrinogen concentrate administration*

- Serious and non-serious adverse events (AE).

1.11 **SAMPLE SIZE CALCULATION**

It has been estimated that, in the control group, 42% of patients will fulfil the primary endpoint (unpublished data from the Pithagore cohort). With an expected percentage of patients in the Clottafact[®] treated group of 27%, the difference between the two groups will be 15%. With a power (1- β) of 90%, a type I error (α) of 5% and a two-

sided test (Z test, unpooled variance), a sample size of 206 patients is needed per treatment group. The rate of drop-out is assumed to be approximately 5%.

Therefore, 434 patients will be included in the study.

As there is some uncertainty about the test Z variance depending itself on the expected rates, the variance is re-estimated in a blind way at 80% of the initially planned sample size (i.e. 80% of 412=326 evaluable patients or 348 patients with adjustment for a 5% dropout rate) to maintain the power to 90% while still considering the same originally planned difference in failure rates, i.e. 15%. Given an estimated overall rate of failures higher than expected, the sample size was re-estimated at 470 patients to maintain the power to 90%. The recruitment period ended on June 30th, 2018 with 448 patients at this date. Based on this sample size of 448, and assuming that 1.55% of patients excluded from the ITT analysis (i.e. patients without receiving at least a dose of the IMP) the current power of the trial is 89.6%, which remains very close to the targeted power of 90%.

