3.3.5.3 Baseline Efficacy Variables

All efficacy variables will be presented by randomisation group. Baseline data are defined as the last available data before the start of IMP infusion.

Date and time of the last available Hb (g/dL) determination will be presented. The month of last recorded Hb value during pregnancy will be mentioned.

Fibrinogen, Hb, Ht and RBCs count will be displayed in the efficacy analysis section in order to display baseline and follow-up results in the same tables.

Exploratory variables are efficacy laboratory data and will be displayed in the efficacy analysis section.

3.3.5.4 *Baseline Safety Variables*

All safety variables will be presented by study treatment group. Baseline data are defined as the last available data before the start of IMP infusion.

All laboratory data except those defined as efficacy variables (in the above section) or as exploratory variables will be defined as safety criteria. All laboratory data will not be displayed in the baseline section but in the analysis of safety in order to display in the same table the baseline and other data.

3.3.5.5 *Investigational Product (IMP) and Concomitant Treatments*

3.3.5.5.1 *Extent of Exposure*

Summary tables will display the number of patients exposed, duration of exposure (in minutes, automatically derived from the start and end times of IMP infusion), in each randomisation group and, if applicable (any error in allocation treatment), in each treatment group.

3.3.5.5.2 *Treatment Compliance*

The delay between the start of prostaglandin infusion and the start of IMP infusion (in minutes) will be presented as a continuous variable.

The same variables will be estimated and presented on the “as treated” set (SS set) in each treatment group.

3.3.5.5.3 *Concomitant Treatment*

Concomitant treatments will be coded using the WHO DDE March 1, 2014 version.

The number and percentage of patients with at least one concomitant medication will be summarised by group. Concomitant medications will be described on SS set by anatomical therapeutic chemical (ATC) name, overall and by group.

3.3.6 *Efficacy analyses*

3.3.6.1 *Primary Efficacy Variable(s) and prognostic factors*

3.3.6.1.1 *Description of the primary efficacy variable(s)*

The primary efficacy variable is a binary composite endpoint (failure versus success). Failure is defined when a patient

- loses at least 4 g/dL of Hb compared to the reference Hb level,

and/or

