- requires the transfusion of at least 2 units of packed RBCs within 48 hours following the administration of IMP.

The reference Hb level is the most recent Hb value recorded during the third trimester of pregnancy.

Raw percentages of failures will be estimated within each treatment group (placebo or Clottafact®).

3.3.6.1.2 *Description of prognostic factors and covariates of the primary efficacy variable(s)*

Baseline fibrinogen will be considered as a major prognostic factor of the primary outcome. Baseline fibrinogen and centre (Centres with small number of enrolled patients (<20 patients) will be pooled arbitrary into one) will be adjusted in the primary model as described below. As the linear relationship between baseline fibrinogen and the primary binary outcome (on the logit scale) is a priori ascertained, baseline fibrinogen will be categorized into four classes (≤ 2 g/L,]2;3] g/L,]3,4] g/L, > 4 g/L).

Other possible prognostic factors will be considered secondarily and listed as follows:

- Other baseline covariates :
 - tranexamic acid intake (Yes/No),
 - lost of at least 2g/dl of haemoglobin (at V1) compared to the reference level (the last assessment during the third trimester),
 - heart rate at the inclusion (<100 beats/min vs. ≥ 100 beats/min)
 - measured/estimated total blood loss volume (<1000 ml vs. ≥ 1000 ml).

Raw percentages of failures will also be provided by centre, by tranexamic acid intake. (Yes versus No), by baseline fibrinogen (categorized into four classes: ≤ 2 g/L,]2;3] g/L,]3,4] g/L, > 4 g/L) and by other covariates levels identified above.

- Post-randomization covariates (within the 48 hours following IMP administration):
 - fibrinogen concentrate as rescue therapy,
 - tranexamic acid intake,

- administration of fresh frozen plasma,
- administration of platelet units,
- haemostatic intervention by bakri balloon,
- haemostatic invasive procedures,
- transfer to intensive care unit,
- heart rate \geq 100 beats/min.

Post-randomization covariates will be mainly used to implement the multiple imputation model for the primary analysis. Although partially confounded with the treatment effect, these post-randomization covariates will also be investigated to check whether they are treatment effect modifiers. Raw percentages of failures will be provided by post-randomization covariates levels.

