Baseline covariates will be tested separately in univariate logistic regression models which will be the primary model to estimate the treatment effect by covariate level with its 95%CI (see §7.4 for SAS code). Forest plots displaying treatment effects (odds ratios) along with their 95%CIs will be displayed across covariates levels.

A multivariate analysis will be done to test in the model the following relevant covariates and interactions. Center, the total blood lost, the tranexamic acid intake, lost of haemoglobin compared to the reference level, heart rate and their interactions will be analysed in a stepwise logistic regression model.

3.3.6.3 *Secondary efficacy variables*

Analyses of secondary efficacy endpoints will be primarily conducted in the ITT set. Sensitivity analyses will be performed in the PP set.

3.3.6.3.1 *Description of secondary efficacy variables*

Secondary efficacy variables are detailed in §1.10.2. We distinguish two types of secondary endpoints:

- **Key secondary efficacy variables :**
 - 1- Calculated and adjustment of total blood loss 48 hours following IMP administration

The calculation and adjustment of total blood loss with regards to transfusional needs will be calculated as follows:

Total blood loss (mL) = blood loss calculated + blood loss compensated by transfusion

With:

-Calculated blood loss = Pregnancy total blood volume x (Ht0 – Htf) x (100/35)

- Pregnancy total blood volume = (Maternal weight measured before pregnancy x 65 mL/kg) x 1.4
- Ht0: last available value of haematocrit before delivery
- Htf: value of haematocrit in the morning of D2

-Blood loss compensated by transfusion (mL) = n RBC x 500mL (with n corresponding to the number of transfused units and 500mL = total transfused blood volume of 300 mL RBC with Ht of 60%).

2- Percentage of patients requiring any need for rescue procedure

The percentage of patients requiring any need for rescue procedure is defined as follows:

- at least one of the following invasive procedure within 48 hours following IMP administration :
 - pelvic arteries embolization,
 - surgical vascular ligation,
 - uterine ligation (B Lynch or other techniques),
 - hysterectomy
 - intrauterine balloon
- and/or administration of recombinant active Factor VII (rFVIIa),
- and/or fibrinogen rescue.

3- Percentage of patients requiring the use of intrauterine balloon within 48 hours following IMP administration.

- **Other secondary efficacy variables :**

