7. SAS CODE

7.1 SAS code fragments for primary analysis of the primary endpoint

The SAS code for the primary model is written as follows:

```

/*****
/* EURAXI PHARMA - SAS version 9.4 Programme created by [name] */
/* Date: 26/10/2018 Last modifications: */
/* Risk level : I Ib */
/* */
/* PROGRAM : F:\Data-Management\01 - Etudes\1016 - Fidel\11 -
Stat\Programmes\1016_FIDEL_EFFICACY_I.sas */
/* */
/* MACRO: %detect, %Stat_des */
/* */
/* Description : PRIMARY ANALYSIS (logistic model) */
/*****

ods graphics on;

ods output ParameterEstimates =_est OddsRatios =_or;
proc logistic data = Main_analysis descending;
class _trt centre _b_fibrinogen(PARAM=REF REF="> 4 g/L") / param=glm;
model _resp = _trt centre _b_fibrinogen /influence iplots;
run;
ods graphics off;

```

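### The primary model leaves out haemoglobin already lost at inclusion, a pre-IMP factor the SAP lists as possibly prognostic, so some power may be given up; the test stays valid

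*SAP*

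**What the plan says.** SAP 3.3.6.2.2 defines the primary analysis as a logistic regression on treatment, centre and baseline fibrinogen in four classes. The code in SAP 7.1 agrees: "model _resp = _trt centre _b_fibrinogen /influence iplots".

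SAP 3.3.6.1.2 introduces further baseline covariates with "Other possible prognostic factors will be considered secondarily and listed as follows". One of them is "lost of at least 2g/dl of haemoglobin (at V1) compared to the reference level". It is used for raw failure rates by level, for the by-level models of SAP 3.3.6.2.6, and for a multivariate analysis in which "lost of haemoglobin compared to the reference level, heart rate and their interactions will be analysed in a stepwise logistic regression model". It may also enter the multiple-imputation model of SAP 3.3.6.2.3.1 if covariate selection retains it.

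The covariate is a true baseline value. Protocol 8.2.1 schedules "Blood sampling for laboratory parameters at inclusion" at Visit 1, and Protocol 8.2.2 places randomisation and the IMP after inclusion. SAP 3.3.5.3 adds: "Baseline data are defined as the last available data before the start of IMP infusion".

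The endpoint counts Hb loss from the last third-trimester value. Protocol 3.2.1 prefers that reference because it is "independent of delivery, PPH and vascular loading".

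**The concern.** The Hb part of the endpoint is the third-trimester value minus a post-IMP value. Hb loss at inclusion is the same third-trimester value minus the Visit 1 value. The two share a term, and whatever was lost before the IMP already counts towards the 4 g/dL threshold. A woman with low Hb at Visit 1 also starts closer to the Hb transfusion objective of 8 g/100 ml (Protocol 7.2), which links the covariate to the transfusion component.

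With a binary outcome, adjusting for a prognostic baseline variable raises the power of the treatment test. It also corrects for chance imbalance between arms in how much Hb had been lost before treatment. Both come without extra patients, which is of some interest in a trial that closed at 448 women against a re-estimated 470. The subset and stepwise analyses could reveal an imbalance but would not change the primary result. Power and precision are at stake, not validity.

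**Working it through.** **1. Reproduce the plan's figures.** The formula for the unpooled Z test is n per group = (1.960 + 1.282)² × [p1(1−p1) + p2(1−p2)] / (p1−p2)², and (1.960 + 1.282)² = 10.507 before rounding.

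- Planning rates of 42% and 27% (Protocol 12.3): 10.507 × 0.4407 / 0.0225 = 205.8, so 206 per group, as stated.
- Re-estimation (SAP 1.11: "the sample size was re-estimated at 470 patients to maintain the power to 90" per cent): the overall failure rate found is not given. Taking 42.5%, so 50% versus 35%, gives 10.507 × 0.4775 / 0.0225 = 222.99, so 223 per group. That is 446 evaluable, and 446 / 0.95 = 469.5, so 470. This matches, and 50% versus 35% is used below.
- Analysed set: 448 × (1 − 0.0155) = 441. Power = Φ(0.15 / √(0.4775 / 220.5) − 1.960) = 89.7%, against 89.6% stated. At 446 it is 90.0%, so the recruitment shortfall costs about 0.3 points.

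**2. Simulate the primary model with and without Hb loss.** From the documents: N = 441, 50% versus 35%, 1:1 allocation stratified by centre, fibrinogen in four classes, two-sided 5%. Assumed: nine centre groups, blocks of 4, fibrinogen class shares of 10/25/35/30%, and a latent-normal outcome. The fibrinogen–outcome correlation (rf) is 0.3 or 0.4. The fibrinogen–Hb loss correlation (rhf) is 0.3 or 0.6, and 0 where Hb loss is unrelated to outcome. There were 6,000 replicates per setting (Monte Carlo standard error about 0.35 points).

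Power in %, SAP model → same model plus continuous Hb loss:

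| Correlation of Hb loss with outcome | rf 0.3, rhf 0.3 | rf 0.3, rhf 0.6 | rf 0.4, rhf 0.3 | rf 0.4, rhf 0.6 |
|---|---|---|---|---|
| 0.3 | 91.6 → 92.4 | 90.9 → 91.3 | 92.3 → 92.9 | 92.1 → 92.4 |
| 0.5 | 91.5 → 94.6 | 91.1 → 93.8 | 92.3 → 95.0 | 93.2 → 94.7 |
| 0.7 | 92.1 → 98.0 | 91.0 → 97.8 | 92.4 → 98.2 | 92.7 → 97.5 |

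At correlation 0 (rhf 0) the results are 91.2 → 91.2 (rf 0.3) and 93.1 → 93.0 (rf 0.4). The unadjusted test averages 89.5%, in line with step 1. The SAP model lies above that because fibrinogen already helps.

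A median split in place of the continuous value (rf 0.3, rhf 0.3) gives 92.0%, 93.9% and 96.9% at correlations 0.3, 0.5 and 0.7, so dichotomising gives back part of the gain.

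**3. Type I error.** With 42.5% in both arms and 8,000 replicates, it is 5.2 to 5.3% for the SAP model and 5.1 to 5.3% with Hb loss added.

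**4. Cross-check by another route.** This is the asymptotic Wald power of a logistic model at N = 441, 50% versus 35%, with a yes/no Hb-loss term and no fibrinogen term. Assuming 30% of women are above the cut, power without the term is 88.7%. With it, power depends on the assumed odds ratio of failure:

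| Odds ratio for Hb loss | Power with term | N for the same power as without it |
|---|---|---|
| 2 | 89.4% | 431 |
| 3 | 90.4% | 417 |
| 5 | 92.1% | 392 |
| 8 | 93.7% | 364 |

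For a class holding 30% of women and 42.5% overall failure, latent correlations of 0.3, 0.5 and 0.7 correspond to odds ratios of about 2.3, 4.2 and 9.5. The two routes therefore agree in pattern, and the 0.7 row needs a very strong predictor.

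**5. Missing Visit 1 Hb.** If women without the value were dropped, the gain at odds ratio 3 would be cancelled once 1 − 417/441 = 5.4% were missing.

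**The case against.** The strongest reply is that nothing here is wrong. The sample size rests on an unadjusted test and claims nothing from covariates, and the planned model reaches about 91 to 93% in the simulation. A short list of pre-specified covariates is good practice. The SAP calls Hb loss only a possible factor, alongside tranexamic acid, heart rate and blood-loss volume, which are also left out. The documents give no estimate of its strength. The simulation suits a linear term and assumes no missing values. A further change would be another departure from the protocol's model, in a SAP dated after recruitment closed.

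Most of this stands as a limit on size. The gain could be under one point, since fibrinogen from the same sampling carries part of the information and a sample drawn during active bleeding may reflect the loss poorly. It does not remove the point. Hb loss differs from the other listed factors because it shares the reference value with the endpoint itself. The documents' reason for preferring third-trimester Hb concerns the choice of reference. Noise in Visit 1 Hb used as a covariate shrinks the gain but adds no bias. The SAP has already revised the protocol's model (fibrinogen classes, pooling of centres), so one more term fixed before unblinding is of the same kind.

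**Conclusion.** The concern holds as a missed gain in efficiency, to be considered rather than required. The primary model omits a pre-IMP variable that is already collected and closely tied to the endpoint. The test keeps its level, and the stated 89.6% power is not undermined. The likely benefit runs from nothing to about 3 points of power for correlations up to 0.5. A gain of 5 points or more would need Hb loss to be an exceptionally strong predictor. These figures rest on assumed correlations, fibrinogen class shares and centre structure, and on no woman being lost for a missing Visit 1 Hb.

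**What to change.** Before unblinding:

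- Add continuous Hb loss at inclusion to the primary model with centre and fibrinogen: reference Hb minus the last Hb before the start of IMP, following the SAP's own definition of baseline.
- State that women with a missing baseline covariate stay in the model, through a missing class or a simple baseline imputation with an indicator, so that no ITT patient with an evaluable endpoint is dropped. SAP 3.3.3 needs a matching exception to its general rule against replacing missing data.
- Report the current model as a sensitivity analysis.

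The cost is SAP wording, one model term and the missing-covariate rule. The odds ratio becomes conditional on one more covariate and lies further from 1. In the simulation its median moves from about 0.50 to 0.49, 0.45 and 0.37 at correlations 0.3, 0.5 and 0.7. The raw failure rates by arm should therefore be reported beside it.

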3.3.6.2 Primary analysis of the primary endpoint

3.3.6.2.1 Hypothesis

- Null hypothesis:

H0: the true failure rate in the Clotfact[®] randomised group = the true failure rate in the placebo group.

- Alternative hypothesis:

H1: the true failure rate in the Clotfact[®] randomised group \neq the true failure rate in the placebo group.

The nominal two-sided level of significance is set to 5%.

The primary analysis will be conducted primarily in the ITT set.

3.3.6.2.2 Model of analysis of the primary endpoint

The primary model of analysis will be a logistic regression to assess the association between a binary exposure variable treatment (variable “_trt”) and the binary outcome (variable “_resp”), adjusting for baseline fibrinogen (variable “_b_fibrinogen”, categorized into four classes (\leq 2 g/L,]2;3] g/L,]3,4] g/L, $>$ 4 g/L) and centre (see SAS code in §7.1). Missing data will be not imputed, assuming the missing completely at random (MCAR) assumption.

The treatment effect (odds ratio of failure) with its 95% confidence interval (95% CIs) will be provided by treatment group and tested at the 5% two-sided level of significance in this model.

Validity of the primary analysis: A graphical analysis of residuals will be done for verifying that assumptions for the primary analysis are met. If adjusting for centre effects lead to convergence issues or unstable estimates, centre effect will be ignored in the analysis.

3.3.6.2.3 *Sensitivity Analyses of the primary endpoint*

3.3.6.2.3.1 Primary sensitivity analysis (MAR assumption)

Assuming the missing at random (MAR) mechanism, multiple imputation (MI) approach by Fully Conditional Specification (FCS) will be used to handle missing data of the primary efficacy endpoint.

A stepwise logistic regression will be done to identify relevant covariates by a backward elimination analysis based on iterative maximum likelihood with the Newton-Raphson algorithm using a significance level of 0.2 to retain variables in the model. Only relevant covariates will be introduced in the MI process. The number of imputations needed will be verified with relative efficiency (RE) for the fully efficient imputation (in unit of variance) and by replicating sets of imputations checking whether the estimates are stable between imputation sets. With a little of missing information (10%), only a small number of imputations are necessary.

The final set of key covariates (referenced here below in the SAS syntax as “key_covariates_for_MI”, see §7.2 for SAS code) to be accounted for in the MI model in addition to treatment and categorized baseline fibrinogen will be defined before breaking the blind.

3.3.6.2.3.2 Secondary sensitivity analysis (MNAR assumption)

All missing data for the primary endpoint will be estimated as failures assuming a missing not at random (MNAR) mechanism. The same model as the one proposed for the primary analysis will be fitted on the new data set considering missing data as failures.

3.3.6.2.3.3 Per Protocol analyses

Same primary model analyses will also be performed in the PP set assuming the MAR, MCAR and MNAR assumptions to handle missing data of the primary efficacy endpoint.

3.3.6.2.4 *Other efficacy analyses of the primary endpoint*

- *Analysis of the baseline fibrinogen as continuous:*

A logistic model will be fitted adjusting linear and quadratic effects of baseline fibrinogen.

- *Analysis of the centre and baseline fibrinogene interactions with treatment:*

Treatment by center and treatment by categorized baseline fibrinogen interactions will be investigated in a logistic regression adjusting for baseline fibrinogen, centre and interactions (see §7.3 for SAS code).

Odds ratios with their 95%CIs will be provided by centre and treatment group and illustrated in forest plots.

3.3.6.2.5 *Individual component analyses of the primary endpoint*

The analysis of the contribution of each component of the composite primary endpoint will be considered as descriptive analyses. Odds ratios and 95%CIs will be provided.

3.3.6.2.5.1 Administration of RBCs from H0 to D2

The percentage of patients requiring the transfusion of at least 2 units of RBCs within 48 hours following IMP administration will be calculated and logistic regression adjusting for baseline fibrinogen value (categorized) will be used to compare the Clottafact[®] group and placebo group.

The same subgroup analyses planned for the primary endpoint will be performed as well.

3.3.6.2.5.2 Percentage of patients losing at least 4g/dL of haemoglobin from H0 to D2

The percentage of patients losing at least 4 g/dL of haemoglobin within 48 hours following IMP administration with regards to the haemoglobin reference level will be calculated. A logistic regression adjusting for baseline fibrinogen value (categorized) will be used to compare the Clottafact[®] group and placebo group.

The same subgroup analyses planned for the primary endpoint will be performed as well.

3.3.6.2.6 *Subset analyses*

Subset analyses will be performed to estimate the percentage of failure by treatment group and by baseline covariates level in ITT and PP sets.

Baseline covariates will be tested separately in univariate logistic regression models which will be the primary model to estimate the treatment effect by covariate level with its 95%CI (see §7.4 for SAS code). Forest plots displaying treatment effects (odds ratios) along with their 95%CIs will be displayed across covariates levels.

A multivariate analysis will be done to test in the model the following relevant covariates and interactions. Center, the total blood lost, the tranexamic acid intake, lost of haemoglobin compared to the reference level, heart rate and their interactions will be analysed in a stepwise logistic regression model.

3.3.6.3 *Secondary efficacy variables*

Analyses of secondary efficacy endpoints will be primarily conducted in the ITT set. Sensitivity analyses will be performed in the PP set.

3.3.6.3.1 *Description of secondary efficacy variables*

Secondary efficacy variables are detailed in §1.10.2. We distinguish two types of secondary endpoints:

- **Key secondary efficacy variables :**
 - 1- Calculated and adjustment of total blood loss 48 hours following IMP administration

The calculation and adjustment of total blood loss with regards to transfusional needs will be calculated as follows:

Total blood loss (mL) = blood loss calculated + blood loss compensated by transfusion

With:

-Calculated blood loss = Pregnancy total blood volume x (Ht0 – Htf) x (100/35)

- Pregnancy total blood volume = (Maternal weight measured before pregnancy x 65 mL/kg) x 1.4
- Ht0: last available value of haematocrit before delivery
- Htf: value of haematocrit in the morning of D2

-Blood loss compensated by transfusion (mL) = n RBC x 500mL (with n corresponding to the number of transfused units and 500mL = total transfused blood volume of 300 mL RBC with Ht of 60%).

2- Percentage of patients requiring any need for rescue procedure

The percentage of patients requiring any need for rescue procedure is defined as follows:

- at least one of the following invasive procedure within 48 hours following IMP administration :
 - pelvic arteries embolization,
 - surgical vascular ligation,
 - uterine ligation (B Lynch or other techniques),
 - hysterectomy
 - intrauterine balloon
- and/or administration of recombinant active Factor VII (rFVIIa),
- and/or fibrinogen rescue.

3- Percentage of patients requiring the use of intrauterine balloon within 48 hours following IMP administration.

- **Other secondary efficacy variables :**

- 1- Change in plasma fibrinogen level (g/L) between H2 and H0
- 2- Change in plasma fibrinogen level (g/L) between H6 and H0
- 3- Change in plasma fibrinogen level (g/L) between D2 and H0
- 4- The same changes will be calculated for Hb, Ht and RBCs
- 5- Duration of haemorrhage (hours): end time of haemorrhage – start time of haemorrhage

- 6- Duration in the obstetrics room (from arrival hour in obstetrics room to delivery hour)
- 7- Duration of hospitalization (from arrival date in obstetrics room to hospital discharge date)
- 8- Number of days in resuscitation and/or intensive care and/or PICU and/or continuous care units (admission date and discharge date)
- 9- Number of days with assisted ventilation

3.3.6.3.2 *Analyses of secondary efficacy variables*

3.3.6.3.2.1 Analyses of key secondary variables

The analyses of key secondary variables will be tested with the Hochberg step-up method:

- 1- Calculated/estimated volume of total blood loss, 48 hours following IMP administration

The estimated/calculated volume of total blood loss 48 hour after IMP administration will be compared between the Clottafact[®] group and placebo group by a t test or non parametric test.

- 2- Percentage of patients requiring any need for rescue procedure

The percentage of patients requiring any need for rescue procedure within 48 hours following IMP administration will be calculated and chi-square or Fisher exact tests will be used to compare between the Clottafact[®] group and placebo group.

- 3- Percentage of patients requiring the use of intrauterine balloon within 48 hours following IMP administration

The percentage of patients requiring the use of intrauterine balloon within 48 hours following the administration will be calculated and chi-square or Fisher exact tests will be used to compare between the Clottafact[®] group and placebo group.

3.3.6.3.2.2 Other analyses of secondary variables

Other secondary endpoints will be analysed in an exploratory purpose.

3.3.6.3.2.2.1 Analyses of the change from baseline in plasma fibrinogen level, Hb and Ht

The evolution in plasma fibrinogen level, Hb and Ht will be analysed at H2, H6 and D2 following IMP administration with a Mixed Model of Repeated Measurements comparing the Clottafact[®] group and placebo group.

3.3.6.3.2.2.2 Analyses of the evolution of haemorrhage

3.3.6.3.2.2.2.1 Analyses of haemoglobin level

- The percentage of patients losing at least 3 g/dL of Hb within 48 hours following IMP administration with regards to the Hb reference level will be calculated and chi-square or Fisher exact tests will be used to compare between the Clottafact[®] group and placebo group.
- The percentage of patients with an occurrence of Hb level < 9 g/dL within 48 hours following IMP administration will be calculated and chi-square or Fisher exact tests will be used to compare between the Clottafact[®] group and placebo group.

3.3.6.3.2.2.2.2 Analyses of the number of units of transfused blood units

The number of units of transfused blood products within 48 hours following IMP administration will be calculated for the Clottafact[®] group and placebo group and compared using a Chi-square or generalized Fisher exact test.

3.3.6.3.2.2.2.3 Duration of haemorrhage

The time to the end of haemorrhage (hours) will be summarised by treatment group. The duration of the haemorrhage will be presented using Kaplan-Meier estimates to the end of haemorrhage. A log rank test will be used to compare the duration of haemorrhage curves between the Clottafact[®] group and placebo group.

3.3.6.3.2.2.3 Description of haemostatic intervention

The percentage of patients with haemorrhage leading to the occurrence of morbidity will be compared by treatment group using Fisher exact test. The percentage of patients requiring at least pelvic arteries embolization, surgical vascular ligation, uterine ligation, administration of recombinant activated Factor VII, intrauterine

ballon, and hysterectomy within 48 hours following the IMP administration will be calculated by group.

The time of intrauterine balloon placement will be described as other haemostatic interventions.

Fisher exact tests will be performed to compare the occurrence of haemostatic interventions by treatment groups.

3.3.6.3.2.2.4 Description of maternal morbidity

The maternal morbidity will be analyzed in the subgroup of patients transferred in resuscitation and/or intensive care and/or PICU and/or continuous care units with:

1. *Duration (days) in resuscitation and/or intensive care and/or PICU and/or continuous care units.*
2. *The maximal SOFA score,*
3. *Duration of admission in obstetrics room (hours), duration of hospitalization and number of days with assisted ventilation*

Chi-square or Fisher exact tests will be performed for categorical data and t test for continuous quantitative data or other appropriate tests (ie non parametric tests).

